Septic shock refers to life-threatening organ dysfunction caused by the body 's uncontrolled response to infection, accompanied by severe circulatory, cellular and metabolic abnormalities. The in-hospital mortality rate is as high as more than 40 % [16], and the proportion is higher in newborns [15]. In the early stage of septic shock, in order to maintain the stability of circulation, a large amount of fluid resuscitation treatment is usually needed. The effective circulating blood volume of the body is supplemented by intravenous infusion and other means, and the increase of stroke volume and cardiac output is promoted, so as to restore the perfusion of tissues and organs, improve their hypoxic state, and then correct septic shock [17]. Therefore, appropriate volume resuscitation is an important measure for clinical treatment of septic shock. How to effectively monitor the volume status of patients and reasonably guide clinical treatment has become the focus of clinical workers. The ' Save Sepsis Campaign ' emphasizes that sepsis and septic shock are clinical emergencies and require early comprehensive treatment. It is recommended to guide late fluid therapy through repeated hemodynamic monitoring after timely initial fluid resuscitation [18,19]. Hemodynamic monitoring in patients with septic shock is mainly used to evaluate whether continuous fluid infusion can improve organ perfusion and assist in deciding whether positive inotropic drugs are needed [17]. At present, non-invasive monitoring and clinical experience are mainly used to roughly judge the organ function, volume status and resuscitation effect of patients. ' Detachment after heavy irrigation ' has become a clinical norm, while empirical diagnosis and treatment can lead to insufficient volume or excessive fluid. Volume overload is often ignored until clinical signs or imaging signs of organ dysfunction occur, and continuous positive fluid balance will significantly increase the complications and mortality of patients [20,21]. Therefore, it is an important way to improve the therapeutic effect and prognosis quality of septic shock by establishing accurate and objective organ function monitoring methods in the process of diagnosis and treatment, carrying out appropriate fluid management optimization under the guidance of

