excessive lung water volume load should be considered. Increases should begin to make adjustments in fluid therapy and respiratory therapy that are most suitable for patients [28]. However, previous studies are basically aimed at adults, and the number of studies in neonates is very limited. In clinical studies, due to the particularity of neonatal anatomy and physiology, there is a lack of research on the application of severe ultrasound technology in fluid resuscitation of neonatal septic shock. [29] There is an urgent need for an effective non-invasive monitoring method to assist fluid resuscitation in children with septic shock.

At present, the fluid resuscitation methods used in our department for neonates with septic shock mainly include : conventional fluid resuscitation, severe ultrasound-guided fluid resuscitation and NICOM-assisted fluid resuscitation. In this prospective observational study, children with neonatal septic shock diagnosed in the neonatal intensive care unit of Guangdong Second People 's Hospital from January 1,2022 to December 31,2023 were included in the study. According to the different monitoring methods used in shock treatment, 30 cases of severe ultrasound-assisted fluid resuscitation, 30 cases of NICOM-assisted fluid resuscitation and 30 cases of conventional fluid resuscitation were collected, a total of 90 cases. The hemodynamic differences, NICU hospitalization time, renal replacement therapy / mechanical ventilation, and 28-day mortality were compared among the three groups to comprehensively evaluate the application value of cardiopulmonary ultrasound and non-invasive cardiac output in fluid resuscitation of neonatal septic shock. Improve the therapeutic effect of neonatal septic shock, enrich the application field of clinical ultrasound, and promote the cross-fusion of ultrasound and pediatrics, and provide clinical basis for subsequent prospective studies.

二、 research objective

1. Main Objective: To study the application value of severe ultrasound and non-invasive cardiac output technique in fluid resuscitation of neonatal septic shock.

2.Secondary purpose: To promote the therapeutic effect of neonatal septic shock and enrich the application field of clinical ultrasound technology.

三、 Research Design Types, Principles, and Test Procedures

1. Research Design

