In this study, children with neonatal septic shock diagnosed in the neonatal intensive care unit of the Second People 's Hospital of Guangdong Province from January 1,2022 to December 31,2023 were included. According to the different monitoring methods used in routine / clinical shock treatment, 30 cases of severe ultrasound-assisted fluid resuscitation, 30 cases of NICOM-assisted fluid resuscitation and 30 cases of routine fluid resuscitation were collected. The demographic data, blood examination and microbiological examination data of the three groups at admission were collected. The fluid volume, blood lactic acid, blood pressure, vasoactive drugs (such as dopamine and epinephrine / norepinephrine), mechanical ventilation, renal replacement therapy and antibiotic use before fluid resuscitation were collected. The cumulative fluid infusion volume during fluid resuscitation (6 hours), and the use of vasoactive drugs and mechanical ventilation for 6 hours were collected. NICU hospitalization time, cumulative hospitalization time and mortality were collected.

四、 case selection

1. Inclusion criteria:

1 Born less than 28 days on admission; 2 Conform to the diagnostic criteria for neonatal septic shock in the ' 2020 International Guidelines for Saving Sepsis Campaign: Management of Septic Shock and Sepsis-related Organ Dysfunction in Children; 3 For children diagnosed with septic shock, fluid resuscitation should be performed according to the routine diagnosis and treatment. 4 The legal guardian has signed the informed consent.

2. excluded criteria:

1 combined with neurogenic shock, trauma and hemorrhagic shock; 2 symptomatic patent ductus arteriosus; 3 combined with congenital heart disease; 4 give up treatment or death within 24 hours of admission; 5 The legal guardian refused to participate in the study; 6 Key information and information missing.

3. Elimination criteria

Subjects who have been enrolled in the study but meet one of the following criteria should be excluded :

(1) After inclusion, those who did not meet the inclusion criteria or met the exclusion criteria were found.

(2) Those who have not used test drugs / interventions.

4. Standard for suspension of research

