(3) The cumulative fluid infusion volume during fluid resuscitation (6 hours), and the use of vasoactive drugs and mechanical ventilation for 6 hours were collected.

(4) NICU hospitalization time, cumulative hospitalization time and mortality were collected.

七、 standards for efficacy appraisal

The main efficacy criteria : NICU hospitalization time and cumulative hospitalization time, mortality.

Secondary efficacy criteria : cumulative fluid volume during fluid resuscitation (6 hours), and use of vasoactive drugs and mechanical ventilation for 6 hours.

八、 Observation of adverse events

Observation of adverse events : Clinicians should evaluate the fluid resuscitation of children at any time during the experiment. If the clinical symptoms and other auxiliary examinations (such as heart rate, liver size, mental state, X-ray, blood gas analysis, etc.) are

inconsistent with the relevant non-invasive examinations, the experiment should be terminated immediately and the superior physician should be found in time to assist.

九、 Data security monitoring

Clinical research will develop a corresponding data security monitoring plan based on the size of the risk. All adverse events were recorded in detail, properly handled and tracked until they were properly resolved or stable. Serious adverse events and unexpected events were reported to the ethics committee, competent authorities, sponsors and drug supervision and management departments in a timely manner according to the regulations. The main researchers regularly conduct a cumulative review of all adverse events, and if necessary, convene a meeting of researchers to assess the risks and benefits of the study ; research that is greater than the minimum risk will arrange independent data monitors to monitor the research data, and high-risk research will establish an independent data security supervisory committee to monitor the accumulated security data and effectiveness data to make recommendations on whether the research will continue.

十、 Statistical processing

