Measurement data and count data were expressed as mean \pm standard deviation [or median (interquartile range)] and percentage (%), respectively. Normal and non-normal distribution data were analyzed by two independent sample t test and Mann-Whitney U test, respectively. The chi-square test was used to compare the count data rates between groups. Kaplan-Meier method was used to draw the survival curve, and Log-rank test was used to compare the difference of 28-day cumulative survival rate between the two groups. Baseline covariates were adjusted in the Cox proportional hazards model to calculate the hazard ratios (HRs) and their 95 % confidence intervals. Logarithmic conversion was performed on hospital stay and organ support time and linear regression analysis was used to calculate a 95 % confidence interval for reporting. No data with missing information is interpolated. The above statistical analysis was performed using R software, and the test was bilateral, and $p < 0.05$ was considered statistically significant.

十一、 Ethics in clinical research

Clinical research will follow the World Medical Congress ' Helsinki Declaration ' and other relevant provisions. Before the study began, the clinical study was carried out after the ethics committee approved the test plan. Before each subject is selected for this study, the researcher has the responsibility to fully and comprehensively introduce the purpose, procedure and possible risks of this study to the subjects or their agents, and to sign a written informed consent form. The subjects should be informed that they have the right to withdraw from the study at any time. Informed consent should be retained as a clinical research document for review. The personal privacy and data confidentiality of the subjects will be protected during the study.

十二、 Research progress

January 1, 2022 - March 31, 2022 : Pre-project preparation, harmonization of data collection standards, training of personnel

From April 1,2022 to May 31,2023 : the specific implementation stage of the experiment, case data were collected.

From June 1,2023 to December 31,2023 : Write scientific research papers and project summary reports 1 Organize research data and conduct statistical analysis ; 2 writing and submission of scientific research papers ; 3 Summarize the research results and write the project summary report.

十四、 reference

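### Hospital stay is a main outcome with no rule for in-hospital death, so a group with more early deaths can appear to do better

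*Combined protocol and SAP*

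**What the plan says.** Section 七 (standards for efficacy appraisal) names the main outcomes: "The main efficacy criteria : NICU hospitalization time and cumulative hospitalization time, mortality". The abstract's list is the same in substance, although it does not attach the word NICU to the first stay outcome. Neither list ranks the outcomes or combines them.

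Section 十 and the abstract give the analysis of stay: "Logarithmic conversion was performed on hospital stay and organ support time and linear regression analysis was used" to give a 95% confidence interval. Measurement data in general are compared by t test or Mann-Whitney U test. Death has its own analysis by Kaplan-Meier and a Cox model, and "Log-rank test was used to compare the difference of 28-day cumulative survival rate" between groups. The end of section 一 (Research background) likewise says that "28-day mortality were compared among the three groups".

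Two other provisions come near the point:

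- Section 四 (case selection) excludes infants who "give up treatment or death within 24 hours of admission".
- Section 十 says of missing values: "No data with missing information is interpolated".

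Neither says whether, for a later death, stay ends at death, is censored, is left out, is scored as worst or is treated as subject to a competing event.

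**The concern.** A short stay is a good result only if the infant went home alive. When stay is analysed as a plain duration, death on day 5 and live discharge on day 5 count the same. If deaths come earlier than usual discharge and mortality differs between groups, the comparison favours the group with more deaths. A monitoring method that saves lives can then look worse on two of the three main outcomes.

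Leaving deaths out is no neutral escape. It compares survivors, a set defined by what happened after baseline, and a group that keeps sicker infants alive may have longer stays for that reason.

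Death is not expected to be rare. The background says of septic shock that "The in-hospital mortality rate is as high as more than 40" per cent, with a higher proportion in newborns. That is a background rate, not a forecast for this cohort.

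**Working it through.** The plan has no figure of its own to reproduce here. It gives no expected stay, time of death or mortality difference, and no power or effect size behind the 90 infants.

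**From the documents.** 30 infants per group; two-sided 0.05; t test, Mann-Whitney or linear regression of log stay; deaths within 24 hours of admission excluded.

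**Assumed.** Survivor stay is lognormal and identical in both groups, median S = 30 days, log SD 0.7. Time to death is lognormal, median D, log SD 0.8, with deaths before 24 hours redrawn. Mortality is p_L in one group and p_H in the other.

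**Formula.** If a death contributes its time to death, the mean of log stay in a group is (1 − p) ln S + p ln D. The geometric mean ratio, lower-mortality over higher-mortality group, is therefore

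ratio = exp[(p_H − p_L) × ln(S/D)] = (S/D)^(p_H − p_L).

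**20% versus 40% mortality, S = 30 days** (10,000 simulated studies per row):

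| Median time to death | Formula | Simulated ratio | Lower-mortality group significantly longer (t on log stay) | Significantly shorter | Significantly longer (Mann-Whitney) |
|---|---|---|---|---|---|
| 6 d | 5^0.20 = 1.38 | 1.37 | 21.9% | 0.0% | 20% |
| 10 d | 3^0.20 = 1.25 | 1.24 | 15.0% | 0.2% | 14% |
| 20 d | 1.5^0.20 = 1.08 | 1.08 | 6.1% | 0.9% | 5% |
| 30 d | 1^0.20 = 1.00 | 1.00 | 2.6% | 2.7% | 2.4% |
| 45 d | 0.667^0.20 = 0.92 | 0.92 | 0.9% | 6.4% | 0.9% |

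Chance alone gives 2.5% in each direction.

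**Smaller gaps, deaths at 6 d.** 30% versus 40%: formula 5^0.10 = 1.17, simulated 1.17, significantly longer in 8%. 10% versus 20%: 1.17 and 9%. Equal mortality, 40% versus 40%: 0.99 and 2.4%, so no bias.

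**Effect of the 24-hour exclusion.** In the 6-day case it removes 1.3% of deaths. Without it the result is 1.38 and 23%; with it, 1.37 and 22%.

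**If deaths are left out instead (20% versus 40%).** Additional survivors make up 0.20/0.80 = 0.25 of survivors in the lower-mortality group. If their stay is k times that of the others, the ratio is k^0.25.

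- k = 1: 1.00, significantly longer in 2.5%
- k = 1.5: 1.11, in 7%
- k = 2: 1.19, in 11%

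**Second set of assumptions.** With survivor median 20 days, log SD 0.6 and deaths uniform over days 1 to 10, 20% versus 40% mortality gives the higher-mortality group a ratio of 0.75. This equals 1/0.75 = 1.33 in the orientation above. That group is significantly better in 24% of runs and significantly worse in 0.1%. If all deaths fall by day 5, the ratio is 0.67 (significantly better in 31%); if they spread to day 28, it is 0.90 (8%).

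**Does a remedy work?** Under the first set of assumptions at 20% versus 40%:

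- A Gray-type test of live discharge, with deaths kept in the risk set, is significant in the wrong direction in at most 0.04% of runs and in the right direction in 35–36%.
- A Mann-Whitney test with deaths ranked worst gives at most 0.07% and 27–28%.
- At equal mortality they reject in 4.9% and 4.7% of runs in total.

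**The case against.** **The size is illustrative, and the lead case is unfavourable to the plan.** It combines a 20-point mortality gap, early deaths and long stays, none of which the documents state. With deaths at 6 days and 20% versus 40% mortality, a survivor median of 20 days gives 1.27 and 17%; 15 days gives 1.19 and about 13%. At 35% versus 40% with a 30-day median, the result is about 1.08 and 5%. If stay runs from admission and 10 days precede shock, the ratio falls to 1.19, although the error rate stays near 20%. All of this stands as a limit on size; the mechanism is unaffected.

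**Other rules might remove dying infants from the stay data.** Section 四 excludes cases with key information missing and suspends the study for cardiac arrest and other serious complications. But it does not say that an infant who dies is thereby left out of the stay analysis. If that were intended, the survivors-only problem would arise instead, with no bias only when the additional survivors stay as long as the others.

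**Mortality is reported beside stay.** A reader could see a conflict, but the stay estimate stays distorted and no rule says how to read the two together. Mortality is also a weak safeguard at this size. For 40% versus 20% with 30 per group, pooled SE = √(2 × 0.3 × 0.7/30) = 0.118 and unpooled SE = √((0.24 + 0.16)/30) = 0.115. Power is Φ[(0.20 − 1.96 × 0.118)/0.115], about 39%.

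**The remedy counts mortality again.** With identical survivor stays, the 35–36% right-direction rate is entirely a mortality signal, and mortality is already a main outcome. This is true and should be stated when results are read. It is the price of a stay outcome that does not reward death.

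**Conclusion.** The concern holds. Stay is a main outcome analysed as a plain duration, and no text covers deaths after 24 hours. The plan as written can therefore give a result in the wrong direction.

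Confidence is high that the rule is missing and that the bias follows when deaths are early and mortality differs. The size is uncertain because it rests on assumed stays, death times and mortality gaps. Across the early-death scenarios with survivor median 30 days and deaths at 6 days, the spurious ratio runs from about 1.08 (35% versus 40% mortality) to 1.37 (20% versus 40%), with wrong-direction significance from 5% to 22%. There is no bias if mortality and timing of death are equal, and the direction reverses if deaths come later than usual discharge.

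This should be fixed before analysis. It does not invalidate the mortality analysis.

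**What to change.** In section 十 and the matching abstract text, replace the stay comparison with one pre-specified primary method:

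- **Suggested:** time to live discharge, separately for NICU and hospital, with death as a competing event. Report cumulative incidence curves, Gray's test and a Fine-Gray model adjusted for the baseline covariates. These are mentioned only for the Cox model and never listed, so list them.
- **Alternative:** a rank test with every death ranked worse than the longest stay.

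The two methods have different estimands, so name one as primary. Also:

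- Define when stay starts.
- Say how an infant is counted who leaves after treatment is given up beyond 24 hours; the protocol pairs this with death only within 24 hours.
- Say how a live NICU discharge followed by death on a ward is counted in each outcome.
- Apply a stated death rule to organ support time, which the same sentence covers.
- Report log stay in survivors as descriptive only, beside mortality.

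**Cost.** Mainly wording. The data need discharge status, alive or dead, beside each stay. If mortality is recorded only to day 28, one field for later in-hospital deaths must be added. The drawback is that a subdistribution hazard ratio or rank effect is less intuitive than a ratio of mean stays.
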